2.2 Secondary Objectives

Not applicable.

2.3 Exploratory Objectives

Not applicable.

3 STUDY DESIGN

[figure not shown]
3.1 Overview of Study Design

This is a cross-sectional observational single-arm cohort study with descriptive data analyses among patients receiving dapagliflozin within the Cegedim Strategic Data (CSD) Longitudinal Databases (LPDs) electronic medical records (EMRs) in Europe. The assessment of combination use with loop diuretics or pioglitazone will incorporate longitudinal follow-up (See Figure 3.1-1). The study will describe the utilization pattern of dapagliflozin during the first three and a half years after marketing authorization and launch in Europe, specifically the countries reporting to this data source: Belgium, France, Germany, Italy, Spain and United Kingdom. This analysis will be repeated at 18, 30 and 42 months from the launch of dapagliflozin (T0, estimated as January 1, 2013).

The "prescription index date" for each patient included in the study will be defined as the date a patient is first prescribed dapagliflozin.

Follow-up of Subjects

The follow-up period will be used to identify concomitant use of dapagliflozin with loop diuretics or pioglitazone. Follow-up will begin on the date a patient is prescribed dapagliflozin, which will represent the beginning of follow-up (i.e., "index date"). Follow-up will continue until the discontinuation of dapagliflozin (i.e., the final day of the days' supply for the last prescription for dapagliflozin). Once a new user of dapagliflozin discontinues his/her treatment at any time (could also include an interruption in treatment), he/she will not be identified for future analyses.

3.2 Study Population

The study population will be new users of dapagliflozin who meet the inclusion and exclusion criteria noted below. For research question 1-3 and 5 only, cross sectional data in new users of dapagliflozin will be used and therefore treatment interruptions are not of concern in these analyses. For research question 4, a follow-up will be performed and treatment interruptions will be dealt with as described in Section 3.1, Follow-up of Subjects.

Eligible study subjects will be selected from the study databases (described in section 3.2.1 and Figure 3.1-1). All subjects meeting inclusion and exclusion criteria and prescribed dapagliflozin within each database will be selected for inclusion for each analysis dataset:

- Patients newly prescribed dapagliflozin between T0 and 18 months meeting the inclusion criteria will be included in analysis 1 dataset.
- Patients prescribed dapagliflozin between T0 and 30 months meeting the inclusion criteria will be included in analysis 2 dataset. This second analysis dataset will include patients newly treated with dapagliflozin between 19 and 30 months and patients from analysis 1 still on treatment with dapagliflozin during the analysis 2 time period. The existing patients from analysis 1 will only contribute to the follow-up period (see section 3.1 for follow-up definition).
- Patients prescribed dapagliflozin between T0 and 42 months meeting the inclusion criteria
 will be included in analysis 3 dataset. This third cohort will include patients newly treated
 with dapagliflozin between 30 and 42 months and patients from analysis 2 still on treatment
 with dapagliflozin during the analysis 3 time period. The existing patients from analysis 2
 will only contribute to the follow-up period (see section 3.1 for follow-up definition).

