1.2 Research Question

Research question 1: What are the baseline characteristics of the patients prescribed dapagliflozin in Europe?

Research question 2: What proportion of patients prescribed dapagliflozin have baseline moderate to severe renal impairment?

Research question 3: What proportion of patients prescribed dapagliflozin are 75 years of age or older at the time of the index prescription?

Research question 4: What proportion of patients prescribed dapagliflozin are also users of loop diuretics or pioglitazone during the baseline period and the available follow-up period?

Research Question 5: What proportion of patients prescribed dapagliflozin does not have a diagnosis of Type II Diabetes during the baseline period or on the index date?

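### For combination use with loop diuretics or pioglitazone, the 30- and 42-month analyses keep earlier new users only if they are still on dapagliflozin, although research question 4 asks about everyone prescribed it

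*Protocol*

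**What the plan says.** Research question 4 (Protocol section 1.2) asks: "What proportion of patients prescribed dapagliflozin are also users of loop diuretics or pioglitazone during the baseline period and the available follow-up period". Section 2.1 frames the primary objective around all new dapagliflozin users and names combination use as one of its subgroups.

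Section 3.2 defines three datasets, for months 18, 30 and 42. The second bullet opens cumulatively: "Patients prescribed dapagliflozin between T0 and 30 months meeting the inclusion criteria will be included in analysis 2 dataset". It then narrows the dataset to new starters of the later window plus "patients from analysis 1 still on treatment with dapagliflozin during the analysis 2 time period", and adds: "The existing patients from analysis 1 will only contribute to the follow-up period". The third bullet does the same for analysis 3, drawing on analysis 2.

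Section 3.1 gives the matching exclusion. Once a new user "discontinues his/her treatment at any time (could also include an interruption in treatment), he/she will not be identified for future analyses". The same section ends follow-up on the last day of supply of the last prescription, and uses follow-up only for the loop-diuretic and pioglitazone question. Section 3.2 says that research questions 1 to 3 and 5 rest on cross-sectional data, so interruptions do not matter for them.

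**The concern.** The question is put for everyone prescribed the drug, but the month-30 and month-42 datasets are conditioned on persistence. They combine all starters of the latest window with those earlier starters who stayed on treatment until it opened. An analysis 1 patient must persist twice to reach analysis 3. If co-use is related to stopping, the later proportions differ from the proportion among all new users. Differences between the three reports would then mix changes in prescribing with attrition.

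Section 3.2 is also inconsistent with itself. Its opening sentences and its restriction define different denominators, and two programmers could reasonably build different datasets. Section 3.1 adds a second conflict: follow-up runs to the end of the last prescription, yet a patient who interrupts and later resumes is removed.

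The study answers a regulatory request (section 1.1) and its results go to the CHMP (section 4.3). Combination use is the only purpose of follow-up.

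**Working it through.** **1. The protocol's own figure.** Table 4.2-1 is T2DM patients × share on oral antidiabetics × yearly uptake (Table 4.2-2, with EU5 uptake for Belgium). UK 2013, for example: 85,000 × 0.572 × 0.003 = 145.9, against 146 in the table. Summed over countries and years this gives 20,325.06, against 20,325 stated, so the forecast reproduces.

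**2. Starters per window.** Assumptions: T0 = 1 January 2013 (section 3.1), starts uniform within each year, and synopsis totals of 1,254, 2,130, 3,318 and 5,960 for 2013 to 2016.

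- Counts read as new starters: months 0–18, 1,254 + 2,130/2 = 2,319; months 18–30, 2,130/2 + 3,318/2 = 2,724; months 30–42, 3,318/2 + 5,960/2 = 4,639. Total 9,682.
- Counts read as prevalent users, with net new users as yearly differences (1,254, 876, 1,188, 2,642): 1,692, 1,032 and 1,915. Total 4,639.

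**3. Share left out of analysis 3.** The protocol gives no stopping rate, so assume an annual stopping probability d with constant hazard h = −ln(1 − d) and starts uniform within a window. The share of a window of w years' starters still on drug at its end is S(w) = (1 − e^(−hw))/(hw). Then

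retained in analysis 3 = n3 + n1 × S(1.5) × (1 − d) + n2 × S(1).

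For d = 0.30, new-starter reading: h = 0.357, S(1.5) = 0.774, S(1) = 0.841. Retained = 4,639 + 1,257 + 2,291 = 8,187, so 1,495 of 9,682 (15.4%) are left out.

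| Assumed annual stopping | New-starter reading: retained (left out) | Prevalent-user reading: retained (left out) |
|---|---|---|
| 10% | 9,155 (5.4%) | 4,303 (7.2%) |
| 30% | 8,187 (15.4%) | 3,700 (20.2%) |
| 50% | 7,325 (24.3%) | 3,185 (31.3%) |

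Section 1.1 expects no French users in these GP data, so the absolute counts are uncertain. The UK rows alone, read as new starters, give 5.1% to 23.2% over the same range of d.

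**4. Effect on the proportion.** Co-use is assumed to be 10% in persisters, with the new-starter reading and d = 0.30. By month 42, 3,296 patients have stopped, and 1,802 of them are still in analysis 3.

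| Assumed co-use in stoppers | All new users since T0 | Analysis 3 as planned |
|---|---|---|
| 20% | (3,296 × 0.20 + 6,386 × 0.10)/9,682 = 13.4% | (1,802 × 0.20 + 6,386 × 0.10)/8,187 = 12.2% |
| 10% | 10.0% | 10.0% |
| 5% | 8.3% | 8.9% |

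The sign of the difference depends on whether stoppers have more or less co-use than persisters.

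**5. Carried-over group versus whole dataset, analysis 2.** Assume 10% of month 0–18 starters co-use and 30% of the others stop before the next window. If 40%, 50% or 60% of co-users stop, co-use in the carried-over group is 0.10(1 − d1)/[0.10(1 − d1) + 0.90 × 0.70] = 8.7%, 7.4% or 6.0%. Adding the 2,724 month 18–30 starters, also at 10%, gives the whole dataset. At 40%: (139 + 272)/(1,600 + 2,724) = 9.5%. At 50% and 60% it is 9.0% and 8.5%. The shift from 10% in the reported figure is therefore 0.5 to 1.5 points.

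**The case against.** The strongest reply is that little is lost. Patients who stop inside the current window remain, because section 3.2 keeps anyone treated during it. Across the scenarios in step 3, including the UK-only one, 45% to 58% of all who stop by month 42 are still in analysis 3. Earlier stoppers were counted in the report current at the time. Analysis 1 does cover every eligible new user up to month 18. The study is descriptive, without significance tests, and the opening sentences of section 3.2 can be read as already cumulative. Figure 3.1-1, to which the text refers, is not visible in the copy reviewed and might help. Section 4.1 leaves analysis detail to the SAP.

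Most of this stands as a limit on the point, but it does not remove it. The restriction is written into the protocol rather than left to the SAP, and section 3.1 repeats it. Nothing in the text restores earlier stoppers or pools the three analyses. That the opening sentences say something else is itself a reason to reconcile the section.

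Three stronger readings are not supported:

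- A reader might infer that the final estimate omits everyone who stopped and must understate combination use. Only those who stopped before the window opened are lost, and step 4 shows that the direction can go either way. Section 1 discusses volume depletion and treatment interruption but draws no link to loop diuretics.
- A reader might see a gap in recruitment, because the second window is "newly treated with dapagliflozin between 19 and 30 months" after a first window ending at 18 months. This is probably ordinary month numbering. A loss of 2,130/12 = 178 patients would also require reading annual users as new starters; on the net-new reading a month is 876/12 = 73.
- Baseline tables limited to each window's starters are not biased by persistence, and their counts can be added across windows.

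**Conclusion.** The point holds for research question 4 only. As written, the month-30 and month-42 estimates describe new starters plus a group selected on persistence, which is not the population the question names. Sections 3.1 and 3.2 also disagree internally on who belongs. The selection follows from the text and needs no assumption. Its size does: the share left out of analysis 3 (about 5% to 31%) rests on assumed annual stopping of 10% to 50%, a constant hazard, uniform starts and the reading of the forecast counts. Neither the amount nor the sign of any bias in the reported proportion can be derived from the protocol; the percentages in steps 4 and 5 are illustrations. Research questions 1 to 3 and 5 are unaffected.

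**What to change.** In sections 3.1 and 3.2, define the research question 4 denominator at each analysis as all eligible new users since T0, each followed from index date to discontinuation or data cut. Keep those who stopped, with the combination use already observed. Report results by entry period and overall, and show the still-treated subset separately with the number who stopped.

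Make the opening sentences of the section 3.2 bullets agree with what follows them and with section 3.1. State for the analysis whether follow-up ends at the last prescription's supply or at a first interruption, since the text now implies both. Word the entry windows so that they are visibly contiguous.

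The cost is rewording two sections and slightly more programming. The data are already held, and no new collection is needed. Finer summaries, such as rates per person-year or cumulative incidence at set times, can be left to the SAP.

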3.2.1 Inclusion Criteria

- 1) Enrolled in the Cegedim databases for at least one year prior to the first prescription of dapagliflozin (baseline time period),
- 2) All patients identified in the database who newly received at least one dapagliflozin prescription during the study period.

3.2.2 Exclusion Criteria

Not applicable.

3.3 Data Source/Data Collection Process

Data Collection Process

This study requires data sources that longitudinally capture patient demographics, prescription information, diagnosis codes, and available laboratory data.

Data Source

The Longitudinal Patient Databases (LPDs) owned by Cegedim Strategic Data include data from 5.8 million active patients in Belgium, France, Germany, Italy, UK and Spain. In the UK, the database is known as The Health Improvement Network (THIN). For this study, data from all six databases/countries will be used assuming dapagliflozin is prescribed in the country.

Physicians using Cegedim proprietary software (Appendix 1) for management of their practice are asked to take part in LPDs. If the practice agrees to participate, they are asked to provide additional services from Cegedim and in return received a discount on the price for their software subscription. Nationally representative panel in terms of age, gender and geographical region are extracted from the pool of all participating physicians using the quota sampling method. All LPD data are strictly anonymous and there is no direct interaction possible with the physician, who is totally free to prescribe any product he/she deems necessary for his/her patient.

The LPDs collect medical information from proprietary practice management software used by the physician during patients' office visits for recording their daily patient interactions in electronic medical records. In each country, a panel of physicians using this software volunteer to make available anonymized, patient-level information from their practices for clinical research purposes. Since these data are being collected in a non-interventional way, they reflect routine clinical practice in these countries. The panel of contributing physicians is maintained as a representative sample of the primary care physician population in each country according to age, sex, and geographical distribution. Whenever a physician leaves the panel, he/she is replaced by another one with a similar profile. Additionally, in most countries, the patient population is representative of the respective country population according to age and sex distribution, as provided by national statistic authorities (Table 3.3-1).

Table 3.3-1: Physician and Patient Populations in the CEGEDIM GP's LPD by Country (2012)

	Belgium	France	Germany	Italy	UK	Spain
Number of physicians in the panel	300	1200	550	700	1780	190
Average number of patients who consulted GP at least once in a year	360,000	1,800,00 0	620,000	700,000	3.200,00	130,000
% of the national population (Eurostat :http://epp.eurostat.ec.europa.eu)	3.24 %	2.76%	0.8%	1.18%	5.04%	0.28%

3.3.1 Content of the Cegedim LPDs

Data are entered during usual patient care and submitted daily to the Cegedim coordinating center, cleaned and de-identified and then made available in the LPDs for research no later than one month after submission. The following anonymized patient data collected from GPs' practice will be extracted from the databases:

- Demographics (Year of birth, gender, registration dates),
- Medical History (Event dates, diagnosis, symptoms, risk factors, co-morbidities, referrals,
- Treatments (indication, molecule/brand, dosage, posology, date and length of prescription),
- Clinical Data (Height, weight, BP, life habits),
- Clinical laboratory tests, X-ray and other investigations (not available in Germany).

The median follow-up duration of a patient in the data base is 27 months in Germany, 36 months in France, 44 months in Spain, 46 months in Belgium, 112 months in Italy and 117 months in UK.

Patient data collected by Cegedim in each country participating in the LPD varies to some extent to accommodate local needs. However, all countries collect data on medical co-morbidities and outcomes, prescriptions, demographics, and physician characteristics. Key metrics of the GPs' LPDs are provided for each country in Appendix 2 (2012 data).

In the LPDs, diagnoses of clinical events are recorded as diagnostic codes (*e.g.* ICD-9, READ). These codes from the different participating countries will be harmonized based on pre-specified algorithms developed prior to the analysis and listed in the statistical analytic plan. Table 3.3.1-1 summarizes the coding conventions for each of the databases.

Table 3.3.1-1: Data Coding Conventions in the Different Countries

	Belgium	France	UK	Italy	Germany	Spain
Drug code dictionary	Association Pharmacologique Belge	Claude Bernard	Multilex	Farmadati	Abdata	Vademecum
Therapy classification	European Pharmaceutical Marketing Research Association (EphMRA)		British National Formulary (BNF)	ATC	ATC	ATC
Disease classification	Cegedim prop thesaurus (mapped	-	Read Codes	ICD-9	ICD-10	CIAP mapped to ICD-9

ATC = Anatomic, Therapeutic, Chemical

ICD = International Classification of Disease

CIAP = International Classification of Primary Care

3.3.2 Content of the Cegedim LPDs for T2DM patients

Table 3.3.2-1 gives approximate estimates of the proportion of T2DM patients captured using the Cegedim LPD in each country.

The total number of T2DM patients in the respective countries during the same period is not known, but may be roughly estimated based on information from the Diabetes Atlas 2012¹ and assuming that this population represents approximately 90 % of the total diabetic population.

Table 3.3.2-1: Estimates of the proportion of T2DM patients captured in Cegedim LPDs (year 2012)

	Source	France	Germany	Italy	Spain	Belgium	UK
Diabetic Population (in thousands)	Diabetes Atlas http://www.idf.org/diabetesatlas	3,493	5,249	3,903	3,249	547	3,336
Estimates of T2DM patients Total Population (in thousands)	0.9 x Diabetic population	3,115	4,724	3,523	2,925	493	3,002
T2DM patients in CegedimLPD s (in thousands)	Cegedim LPD	65	37	42	14	13	118
% of T2DM population in Cegedim LPDs:	T2DM patients in Cegedim LPDs/Estimates of T2DM patients Total Population	2.1%	0.8%	1.2%	0.5%	2.6%	3.9%

Date: 13-Nov-2013

Key metrics for the T2DM patients in GP's LPDs are provided for each country in Table 3.3.2-2.

Information collected during the course of one year (2012), on serum creatinine and eGFR for T2DM patients is detailed in Table 3.3.2-3.

These data, when insufficiently documented in the course of one year, can be extracted over an extended period of time (two years) in patients' medical record in order to add information and increase possibilities for meaningful analyses.

In addition, this information can be complemented in each country by a search of patient's medical records with a list of diagnostic codes identifying chronic kidney disease, renal failure, end-stage renal disease and related diagnoses (according to Wan J. et al² and Denburg M.R., et al³.)

Table 3.3.2-2: Key Data Metrics of T2DM Patients in GP's LPDs

	France	ITALY	UK	GERMANY	SPAIN	BELGIUM
GENERAL DATA						
Number of patients having visited a physician	100,00%	100,00%	100,00%	100,00%	100,00%	100,00%
Of which Male	58,0%	51,9%	55,2%	51,8%	53,8%	53,4%
Female	42,0%	48,1%	44,8%	48,2%	46,2%	46,6%
BIOMETRIC DATA	19					
Number of patients with a weight recorded (1 year history)	56,0%	39,9%	83,5%	29,1%	28,3%	37,3%
Number of patients with height recorded (1 year history)	20,6%	39,6%	30,8%	28,3%	23,2%	13,9%
Number of patients with BMI recorded (1 year history)	20,2%	39,4%	29,0%	28,2%	20,7%	13,2%
Number of patients with BMI recorded (3 years history + calc)	40,0%	62,7%	54,0%	32,1%	77,5%	24,4%
Number of patients with waist recorded (1 year history)	1,2%		0,4%			
Number of patients with Blood Pressure recorded (1 year history)	64,8%	54,5%	91,6%	28,2%	40,9%	73,4%
average records by year by patient	3,34	2,73	2,80	5,72	2,44	4,4
BIOLOGICAL EXAMS	500 800		- 20			
Number of patients with a fasting blood glucose test	29,5%	67,7%	45,6%	54,5%	44,1%	68,5%
Number of patients with a Hba1c rate	43,2%	66,4%	88,0%	77,1%	27,5%	53,6%
Number of patients with Total cholesterol	26,7%	61,2%	83,8%	57,2%	0,0%	56,4%
Number of patients with LDL	26,8%	55,4%	55,9%	54,1%	26,5%	53,1%
Number of patients with HD L	26,0%	58,3%	74,7%	52,8%	27,7%	55,9%
Number of patients with Triglycerid	27.2%	60,3%	63,9%	56,6%	41,8%	56,1%

Table 3.3.2-3: Information collected on serum creatinine and eGFR for T2DM patients in Cegedim LPDs during the course of one year (year 2012)

	FRAN	NCE	GERM	ANY	ITA	LY	SPA	IN	BELG	IUM	UK	
Number of patients in the panel	1 800	000	620 (000	700 (000	130	000	360 (000	3 200	000
T2DM patients (% of panel population)	65 000	4%	37 000 6% 42 000 6%		14 000 11%		13 000	4%	118 000	4%		
T2DM patients:												
with creatinine values recorded	20 500	32%	26 600	72%	25 000	60%	5 700	41%	7 350	57%	105 000	89%
with eGFR values recorded or calculated*	12 300	20%	19 300	52%	20 850	50%	4 200	30%	1 100	9%	93 300	79%

^{*}eGFR estimated using the Cockcroft-Gault (Appendix 5) or MDRD estimation formula (Appendix 4)

3.4 Definitions of Study Variables

Demographic, medical history, treatment, clinical and clinical laboratory data on patients included in this study will be collected from each database.

3.4.1 Outcomes/Endpoint Variables

Table 3.4.1-1 includes the characteristics and definitions of how dapagliflozin users will be categorized and described.

Table 3.4.1-1: Categorization of Dapagliflozin Users

Characteristic	Definition
Patient Demographics, at initiation of dapagliflozin use:	
Age categories	< 45, 45-59, 60-74, >= 75
Sex	Male or Female
Country	Belgium, France, Germany, Italy, Spain, United Kingdom
Concomitant medications before, at initiation of and	Loop diuretics (ATC code C03Cx)
during dapagliflozin use 1	Pioglitazone (Actos, Glustin) (ATC code A10BG),
	Biguanides (ATC Code A10BA)
	Sulfonamide derivates (ATC code A10BB and A10BC)
	Dipeptidyl peptidase 4 inhibitors (DDP4) (ATC code A10BH)
	Glucagon-like peptide 1 (GLP-1, exenatide, liraglutide, ATC code A10BX),
	Alpha glucosidase inhibitors (ATC code A10BF).
	Insulin (ATC code A10A)
Concomitant co-morbidities, at initiation of dapagliflozin use:	
Baseline history of moderate renal impairment	CrCl or eGFR ² value between 30-60 within 12 months prior to the dapagliflozin dispensing
Baseline history of severe renal impairment	CrCl or eGFR value < 30 within 12 months prior to the dapagliflozin dispensing
Baseline history of renal failure	Diagnosis codes for end stage renal disease or dialysis (see Appendix 3)
Congestive heart failure	Diagnosis codes for congestive heart failure (see Appendix 3)
Hypertension	Diagnosis codes for hypertension (see Appendix 3)
Type 2 Diabetes Mellitus, at initiation of dapagliflozin use:	Diagnostic code for T2DM within 12 months prior to the dapagliflozin dispensing (see Appendix 3) OR
	Prescription for an antiglycemic medication within 12 months prior to the dapagliflozin dispensing

Table 3.4.1-1: Categorization of Dapagliflozin Users

Characteristic	Definition
Dapagliflozin Dose, at initiation of dapagliflozin	10 mg
use:	5 mg
Off-Label Use	Patients meeting one of the following criteria:
	 17 years old or younger on index date
	• 75 years of age or older on index date
	 No diagnostic codes for Type 2 Diabetes Mellitus, at or before the initiation of dapagliflozin use (see definition above)
	• Baseline history of moderate renal impairment (see definition above)
	• Baseline history of severe renal impairment (see definition above)
	• Baseline history of renal failure (see definition above)

^[1] Pioglitazone sales are suspended in France and Germany

Estimated creatinine clearance (CrCl) will be calculated by means of the Cockcroft-Gault formula if it is not available in the database. (Appendix 5)

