Study Population: All patients identified in the database(s) who newly received at least one dapagliflozin prescription during the study period. Dapagliflozin use will be representative of the uptake of dapagliflozin in the respective countries.

Data Collection Methods: Cegedim Strategic Data (CSD) Longitudinal Patient Databases (LPDs) come directly from physicians' EMR. Participating physicians use CSD-provided software to record their daily patient interactions and data are transmitted regularly to the Cegedim coordinating center where they are cleaned and de-identified.

Data Sources: CSD's LPDs include data from 5.8 million active patients. Over 4,000 general practitioners (GPs) in six European countries (Belgium, France, Germany, Italy, Spain and United Kingdom) are part of the LPD panels.

Patient metrics in the LPDs include Demographics (Year of birth, gender, registration dates), Medical History (Event dates, diagnosis, symptoms, risk factors, co-morbidities, referrals), Prescription (Rx dates, indication, therapeutic class, molecule, brand, dosage, posology, duration), Clinical Data (Height, weight, BP, life habits) and laboratory data.

Exposures: A patient will be identified as newly exposed when he/she has at least one dapagliflozin prescription recorded in the study database(s).

Outcomes: Outcomes include but are not limited to:

- Patient demographics: age, sex, country,
- Baseline history of type 2 diabetes,
- Baseline history of moderate or severe renal impairment,
- Concomitant medications at baseline and during dapagliflozin use.

Follow-up: Follow-up will begin on the date a patient is first prescribed dapagliflozin, which will represent the beginning of follow-up (i.e., "index date"). Follow-up will continue until the end of study or discontinuation of dapagliflozin (i.e., the final day of the days' supply for the last prescription for dapagliflozin). Follow-up will only be used to determine combination use with loop diuretics or pioglitazone. The baseline period is defined as the 12 months in the database preceding the index date.

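### Table 3.4.1-1 defines concomitant drugs by ATC group, but only three of the six databases classify therapy by ATC; define the rows, above all the two for research question 4, by active substance

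*Protocol*

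**What the plan says.** Protocol Section 3.4.1, Table 3.4.1-1, sets out how dapagliflozin users are to be categorised. The concomitant-drug entry opens "Concomitant medications before, at initiation of and" and continues to cover the period of dapagliflozin use. Its rows pair a drug or class name with an ATC code:

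- "Loop diuretics (ATC code C03Cx"
- "Pioglitazone (Actos, Glustin) (ATC code A10BG"
- "Glucagon-like peptide 1 (GLP-1, exenatide, liraglutide, ATC code A10BX"

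The first two feed research question 4 (Section 1.2): "What proportion of patients prescribed dapagliflozin are also users of loop diuretics or pioglitazone during the baseline period and the available follow-up period". The same combination use is a named subgroup of the primary objective (Section 2.1) and the only purpose of follow-up (Section 3.1).

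Table 3.3.1-1 in Section 3.3.1 gives the coding conventions by country. Therapy classification is ATC for Italy, Germany and Spain and "British National Formulary (BNF" for the UK. The entry spanning Belgium and France reads as EphMRA; that part of the table is broken in the text at hand, so the span is inferred from the layout.

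Treatments are also recorded below class level. Section 3.3.1 lists "Treatments (indication, molecule/brand, dosage, posology, date and length of prescription", and the synopsis has the matching "Prescription (Rx dates, indication, therapeutic class, molecule, brand, dosage, posology, duration".

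**The concern.** A variable meant to be described across six countries should be selected by a rule that can be run in all six. Here the rule is written in a classification that the protocol's own coding table assigns to three of them. In the other three, someone must translate C03C, A10BG or A10BX into another system, and the result depends on choices the protocol does not state.

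There is a second looseness. The rows name particular molecules or brands but attach a whole ATC group. They list no code for fixed-combination products and do not say that dapagliflozin itself is left out.

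The stake is research question 4. The study is part of a risk management plan and was requested by regulators (Section 1.1). Any product containing a loop diuretic or pioglitazone that the selection misses lowers the reported proportion, which is the falsely reassuring direction. Country differences could then partly reflect coding systems rather than prescribing.

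**Working it through.** The protocol states no figure for this point that could be reproduced. The check sets its tables side by side.

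**1. Where the stated rule can be run.** Therapy classification (Table 3.3.1-1) against type 2 diabetes patients in the panel (Table 3.3.2-1, thousands) and forecast dapagliflozin users 2012-2017 (Table 4.2-1):

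| Country | Therapy classification | T2DM patients (thousands) | Forecast users |
|---|---|---|---|
| UK | BNF | 118 | 2723 |
| France | EphMRA (apparent) | 65 | 9246 |
| Belgium | EphMRA (apparent) | 13 | 1111 |
| Italy | ATC | 42 | 2728 |
| Germany | ATC | 37 | 3871 |
| Spain | ATC | 14 | 646 |
| Total | | 289 | 20325 |

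Share in databases not listed as ATC:

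- T2DM patients: (118 + 65 + 13) / 289 = 196 / 289 = 68%.
- Forecast users: (2723 + 9246 + 1111) / 20325 = 13080 / 20325 = 64%.

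Section 1.1 expects no users from France. Without France:

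- T2DM patients: (118 + 13) / (289 - 65) = 131 / 224 = 58%.
- Forecast users: (2723 + 1111) / (20325 - 9246) = 3834 / 11079 = 35%.

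The forecast basis probably understates the UK's weight. As of November 2013, Section 1.1 reports reimbursement achieved in the UK, not achieved in Belgium, limited to 2013 in Germany, and undetermined in Italy and Spain. It confines the missing-data sensitivity discussion to UK data for that reason.

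**2. Pioglitazone row.** A footnote to Table 3.4.1-1 says sales are suspended in France and Germany. Of the four remaining countries (UK, Belgium, Italy, Spain), only Italy and Spain classify therapy by ATC.

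**3. Whether a mapping is promised.** The harmonisation algorithms that Section 3.3.1 defers to the SAP concern diagnostic codes. The protocol states none for drug codes.

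**4. How the rows read.** The sulfonamide row gives two codes, A10BB and A10BC, so the table adds codes where more than one group is meant. A row with one code is naturally read as complete.

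**5. What under-inclusion would do.** Let f be the share of true users of pioglitazone or a loop diuretic who receive it only in products classified outside the listed group. Then reported proportion = true proportion x (1 - f), a relative understatement of exactly f. At f = 0 there is none. The protocol gives no f, does not mention fixed combinations and does not reproduce the ATC index, so f cannot be bounded from it and would differ by country. The formula applies where selection is by the ATC group. Elsewhere even the direction depends on the translation chosen.

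**The case against.** The strongest reply is that product-level drug lists are ordinary SAP content. Section 4.1 says the SAP will elaborate the protocol's analyses and be final before the first extraction. The table names the intended drugs, the databases record molecule and brand, and nothing says fixed combinations are excluded. A competent programmer could carry out the intent in every country. This stands in part: the absence of full code lists from the protocol is not a fault. But the protocol does state specific codes, in a system half of its databases do not use. A SAP that follows them literally cannot be run in the UK, and one that departs from them is at odds with the protocol's table.

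Two stronger readings are tempting, and the documents support neither.

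- A reader might infer that the GLP-1 row would flag every patient because A10BX contains dapagliflozin. The protocol never gives dapagliflozin's ATC code or the contents of A10BX. Even if the group does contain it, the row names the class and two molecules and sits under concomitant medication, and a new user cannot have the drug in the period before initiation. The outcome is unlikely in practice. What remains is that no exclusion is written.
- A reader might infer that A10BG and C03C do miss fixed combinations and so understate research question 4. That depends on the ATC index, which is not in the documents. It is a matter to check, not an established bias.

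The GLP-1, metformin and DPP-4 rows also lie outside research question 4 and are background description.

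**Conclusion.** The concern holds as a mismatch between the stated definition and the data sources. Table 3.4.1-1 fixes concomitant drugs, including both drugs of research question 4, by ATC group, while Table 3.3.1-1 lists ATC for three of six databases. The rule cannot be applied as written in the UK or, if the broken table is read correctly, in Belgium and France. Those databases hold 58% to 68% of the panel's T2DM patients and 35% to 64% of forecast users, the lower figure of each pair leaving out France.

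The effect on the reported proportions cannot be sized. Understatement of combination use is conditional on relevant products being classified outside the listed groups, and its amount is unknown and country-dependent. The two rows for research question 4 matter most. Defining rows by substance is better than the stated method whatever the ATC index shows, because the variable then matches the wording of the question and works the same way in all six databases.

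**What to change.** Before the first extraction, revise Table 3.4.1-1, starting with the loop-diuretic and pioglitazone rows:

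1. Define each concomitant-drug row by active substance, using the molecule/brand field.
2. State that any product containing the substance counts, including fixed combinations.
3. Restrict the GLP-1 row to named GLP-1 agonists and exclude dapagliflozin explicitly.
4. Map each row to each country's own drug dictionary as listed in Table 3.3.1-1, in the SAP or an appendix. ATC codes can stay as an aid where the database uses them.
5. Check the listed ATC groups against the index in force, to see which products the present codes would have included or missed.

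The cost is a table edit and slightly more mapping work. One fixed-combination prescription will count in two drug rows. That is intended and should be footnoted, since the rows will then not be mutually exclusive.
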